6.5.1.2 MQoL Scores by EQMA During the DBT and OLE Phases

The table of MQoL total, domain, and overall change (Question 16) scores at 24 hours postdose by EQMA is provided for the DBT efficacy analysis set by treatment group/OL rimegepant and

overall after (1) the single EQMA in the DBT Phase, and (2) each of the first 5 EQMAs ≥ 23 hours apart in the OLE Phase. Results support exploratory objectives #1 and #2.

For the single EQMA in the DBT Phase, analyses are based on the DBT efficacy analysis set with MQoL eDiary measurement dates in the DBT Phase analysis period.

For the first 5 EQMAs ≥ 23 hours apart in the OLE Phase, analyses are based on OLE efficacy analysis set with MQoL eDiary measurement dates in the OLE outcomes research analysis period.

Refer to the Core SAP for the calculation of the MQoL total and domain scores, and TLF contents.

6.5.1.3 *MQoL Overall Change in Migraine Symptoms During the OLE Phase Using Model Estimation*

Analyses are based on the first 5 EQMAs ≥ 23 hours apart in the OLE Phase for the OLE efficacy analysis set with ≥ 1 MQoL in the OLE outcomes research analysis period.

A linear mixed effects model with repeated measures and the following attributes is used:

- Variables: MQoL Question 16 value as the dependent variable; imputed randomization stratum, categorical EQMA (i.e., 1 to 5 of the OLE Phase), rescue medication or intervening OL rimegepant use at or before the MQoL Question 16 value (yes, no), and migraine attack-by-rescue medication/intervening OL rimegepant use as fixed effects. If there are sparse data within a randomization stratum, then this variable may be excluded.
- Covariance structure for repeated measures accounting for within-subject correlated errors: unstructured. If the model fails to converge or cannot be fit with an unstructured covariance structure, then a first-order autoregressive with homogeneous variances ("AR(1)") structure is used.
- Standard error (SE) estimation method: Huber-White "sandwich" (refer to the Core SAP).

The table displays the following model estimates by EQMA: least-squares mean (LSM), SE, and 95% CI. See Section 9.3.2 for the SAS code.

A line plot with error bars displays the LSM MQoL overall change in migraine symptoms on the y-axis versus EQMA during the OLE Phase on the x-axis by rescue medication/intervening OL rimegepant use at or before the MQoL Question 16 value (yes, no). Error bars denote 95% CIs for LSMs.

6.5.2 *MSQ*

The MSQ consists of 14 items across the following 3 domains: (1) restrictive role function, (2) preventive role function and (3) emotional function.

090177e1a38e3121Approved\Approved On: 15-May-2025 18:57 (GMT)

The table of values and changes from baseline in scores is provided by treatment group/OL rimegepant and overall for each domain for the OLE efficacy analysis set at the following time points: baseline; Week 12 of the OLE outcomes research analysis period. Results support exploratory objective #15.

The frequency table of MSQoL domain score increase from baseline categories is provided by treatment group and overall for the OLE efficacy analysis set at Week 12 of the OLE outcomes research analysis period.

6.5.3 MIBS

The MIBS is a 4-item, patient-administered questionnaire that measures interictal migraine-related burden in 4 domains (impairment in work or school, impairment in family and social life, difficulty making plans or commitments, and emotional/affective and cognitive distress) in the past 4 weeks on days when subjects are not having an attack.

The table of values and changes from baseline in scores is provided by treatment group/OL rimegepant and overall for each domain for the OLE analysis set at the following time points: baseline; Weeks 4, 8, and 12 of the OLE outcomes research analysis period.

Results support other secondary objective #5.

7 CONVENTIONS

Conventions may be further modified in dataset specifications documents instead of the SAP as needed.

7.1 Derived Dates

Derived dates are defined as follows:

- eDiary measurement date: derived for each record in the raw eDiary as follows:
 - eDiary reported study medication date if nonmissing, for any parameter in the Migraine question category at the time of study drug dosing (see Section 7.4.1.1)eDiary manual DCF study medication date, if nonmissing in the Manual DCF Study Medication question category (see Section 7.4.1.2)
 - eDiary finding date otherwise.
- DBT Phase start date: earlier of the RTSM randomization date or DB study drug date. This is an analysis period reference date.
- Study drug date/time: derived from either of the 2 following eDiary sources:
 - Reported: nonmissing eDiary reported study medication date/time (see Section 7.4.1.1)
 - Manual DCF: nonmissing eDiary manual DCF study medication date (see Section 7.4.1.2)

- Study drug start date/time: earliest study drug date/time. This is an analysis period reference date.
- Study drug end date: latest study drug date
- Study drug last date:
 - Before the final database lock: study drug end date derived only for subjects who have either (1) or (2):
 - (1) “yes” or “no” response to the question “Did the subject complete the DBT Phase?” from the DB Subject Status CRF, and “no” response to the question “Will the subject continue into the OLE Phase?” from the DB Subject Status CRF, and missing OL rimegepant start date
 - (2) “yes” or “no” response to the question “Did the subject complete the OLE Phase?” from the OLE Subject Status CRF
 - Final database lock: study drug end date

This is an analysis period reference date.

- First OL wallet dispensed date: earliest nonmissing wallet dispensed date with valid OL wallet ID from the Drug Accountability CRF (see Section 6.2.6.1)
- DB study drug date/time: earliest study drug date/time, if any of the following is met:
 - Earliest study drug date is before the first OL wallet dispensed date
 - Earliest study drug date is equal to the first OL wallet dispensed date, and $00:00 \leq$ earliest study drug time $< 07:00$. First OL wallet dispensed date is missing.

This is an analysis period reference date. DB study drug date/time can be either reported (time is not missing) or manual DCF (time is missing).

- OL rimegepant date/time: study drug date/time (1) with study drug date on or after the first OL wallet dispensed date and (2) not classified as the DB study drug date/time. Note that although rare, it is possible for subjects to have multiple records on the same date. OL rimegepant date/time can be either reported (time is not missing) or manual DCF (time is missing).
- OL rimegepant start date/time: earliest OL rimegepant date/time. This is an analysis period reference date.
- OL rimegepant end date: latest OL rimegepant date. This is used to define OL rimegepant exposure.
- OL rimegepant last date:
 - Before the final database lock: OL rimegepant end date defined only for subjects with “yes” or “no” response to question “Did the subject complete the OLE Phase?” from the OLE Subject Status CRF.
 - Final database lock: OL rimegepant end date.

This is an analysis period reference date.

- DB or OL rimegepant start date/time: study drug start date/time for subjects whose as-treated DB treatment group is rimegepant; OL rimegepant start date/time for subjects whose as-treated DB treatment group is placebo. This is an analysis period reference date.
- DB or OL rimegepant end date: study drug end date for subjects whose as-treated DB treatment group is rimegepant; OL rimegepant end date for subjects whose as-treated DB treatment group is placebo
- DB or OL rimegepant last date: study drug last date for subjects whose as-treated DB treatment group is rimegepant; OL rimegepant last date for subjects whose as-treated DB treatment group is placebo. This is an analysis period reference date.
- OLE Phase start date: earlier of (1) DBT EOT visit date from the Visit Date CRF, or (2) OL rimegepant start date. This is an analysis period reference date.
- OLE Phase end date: latest of (1) OLE Phase start date, (2) OL rimegepant end date, or (3) latest complete visit date on or after the OLE Phase start date through the Week 12/EOT visit date (excluding the Follow-Up Week 2 visit date) from the Visit Date and Unscheduled Visit Checklist CRFs
- OLE Phase last date:
 - Before the final database lock: OLE Phase end date defined only for subjects with nonmissing study drug last date
 - Final database lock: OLE Phase end date.This is an analysis period reference date.
- First DBT rescue medication date/time: This date is used to assess the key secondary efficacy endpoint of rescue medication use through 24 hours postdose during the DBT Phase and the RM=F algorithm during the DBT Phase, and is derived using the following steps:
 - Records that meet the definition of DBT rescue medication are selected with both nonmissing medication date and time (see Section 6.2.6.3).
 - The earliest medication date/time is selected.Note that date and time are not imputed.
- Imputed first DBT rescue medication date/time: This date is used to assess exploratory time-to-event efficacy endpoints during the DBT Phase, and is derived using the following steps:
 - Records that meet the definition of DBT rescue medication are selected with non-missing medication date (see Section 6.2.6.3).
 - If medication time is missing, then time is imputed as follows:
 - If medication date = DB study drug date and DB study drug time is non-missing, then medication time = DB study drug time.
 - Otherwise, medication time is set to “00:00”.
 - The earliest medication date/time is selected.Note that date is not imputed.

- Last contact date: (1) earliest complete death date from AE CRFs, if it exists; (2) otherwise, the maximum complete date of the following: AE start or end; ECG; eDiary finding; eDiary manual DCF study medication; eDiary reported study medication; informed consent; RTSM randomization; laboratory collection; nonstudy medication start or end; OLE Phase eligibility contact; physical measurement; procedure; rating scale; rescue medication; questionnaire; vital sign; visit. If the last contact date is after the most recent raw database creation date, then it is set to the most recent raw database creation date.
- Death date: refer to the Core SAP.

No imputations are performed on these derived dates unless otherwise specified.

Missing time is considered to be earlier than nonmissing time on the same date.

Refer to the Core SAP for the definition of complete dates.

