6.4.4. Rescue Medication

Rescue medication is recognized acute migraine concomitant medication (see [Section 16.3](#), [Appendix 3](#)) used for the management of persistent migraine-related symptoms as per standard of care following dosing with study drug.

The use of rescue medication is NOT permitted within 2 hours of dosing study drug.

In the DBT Phase, rescue medication includes acute migraine medication (permitted or exclusionary) (see [Section 16.3](#), [Appendix 3](#)) dosed after blinded study drug (rimegepant 75 mg ODT or matching placebo) **AND** prior to 48 hours postdose and completion of the 48-hour assessments within the eDiary.

In the OLE Phase, rescue medication includes acute migraine medication (permitted or exclusionary) (see [Section 16.3](#), [Appendix 3](#)) dosed after open-label study drug (rimegepant 75 mg ODT) **AND** prior to 24 hours postdose and completion of the 24-hour assessments within the eDiary.

All non-study medications used as rescue (i.e., for the management of unresolved migraine-related symptoms following primary treatment with study medication [blinded or open-label]) (permitted or exclusionary) must be recorded on the Rescue Medication paper diary. All other non-study drugs should be recorded on the Concomitant Medication paper diary.

Study medication (blinded or open-label) is not permitted to be used as rescue medication.

All dosing of rescue medication (permitted or exclusionary), as defined above, is to be recorded on the Rescue Medication paper diary.

Permitted acute migraine medications are presented in [Section 16.3](#), [Appendix 3](#).

Non-permitted acute migraine medication include: opioids, ergotamines, lasmiditan, triptans, ubrogepant, barbiturates/barbiturate-containing products, and muscle relaxants (except baclofen) and other CGRP antagonists. A full list of restricted and exclusionary medications is located in [Section 16.1](#), [Appendix 1](#).

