6.2.6.3 Nonstudy Concomitant Medications

Frequency tables of the following nonstudy medications are provided by treatment group:

- DBT concomitant for the DBT safety analysis set: all; prophylactic migraine
- DBT rescue medications for the DBT efficacy analysis set.

Medications are displayed in descending order of rimegepant frequency within therapeutic class and preferred name.

The frequency table of nonstudy post-DBT pre-OL rimegepant medications is provided by treatment group and overall for the interim safety analysis set. Medications are displayed in descending order of overall frequency within therapeutic class and preferred name.

Frequency tables of the following nonstudy medications are provided by treatment group/OL rimegepant and overall:

- OL rimegepant concomitant for the OL rimegepant safety analysis set: all; acute migraine; prophylactic migraine
- OLE rescue medications for the OLE migraine analysis set.

Medications are displayed in descending order of overall frequency within therapeutic class and preferred name.

Prophylactic migraine medications are displayed by preferred name without therapeutic class.

The by-subject listing of nonstudy medications is provided by therapeutic class and preferred name for the enrolled analysis set. Acute migraine, prophylactic migraine, and rescue medications are identified. For rescue medications, the medication date/time is displayed instead of the medication start and end dates. The listing also displays abbreviated medication types comma-concatenated in the following order: previous ("P"); current ("C"); DBT concomitant ("D"); post-DBT pre-OL rimegepant ("T"); OL rimegepant concomitant ("O"); follow-up ("F"). A medication may be classified into multiple medication types. See Section 7.6 for the definition of the last 4 medication types.

Refer to the Core SAP for the following: counting rules in nonstudy medication frequency tables; non-study medication start and end date imputation; and definition of previous and current medication types.

Note that medications on the Rescue Medication CRF are collected with both medication date and time (where time may be missing), but not start and end dates. Imputed start and end dates for Rescue Medication CRF data are used only to derive nonstudy medication type.

Nonstudy Medications

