Nonstudy medications are identified from the (1) Triptan-Unsuitable Criteria CRF, (2) Concomitant Medications CRF, or (3) Rescue Medications CRF. The Concomitant Medications CRF collects indications, and links medical history and AE terms respectively to the Medical History and AE CRFs.

Migraine Standard of Care Medications

Acute migraine-specific medications are defined as nonstudy medications with preferred name containing triptan, ergotamine, lasmiditan, or ubrogepant.

Acute migraine medications are defined as any of the following nonstudy medications:

- Acute migraine-specific medication
- Those with an indication of “acute migraine medication” from the Concomitant Medications CRF
- Those from the Rescue Medications CRF.

Prophylactic migraine medications are defined as nonstudy medications with an indication of “prophylactic migraine medication” from the Concomitant Medications CRF.

Migraine standard of care medications are defined as acute migraine or prophylactic migraine medications.

DBT Rescue Medications

DBT rescue medications are defined as DBT concomitant medications from the Rescue Medications CRF that meet any of the following criteria:

- $DB \text{ study drug date/time} < \text{medication date/time} < DB \text{ study drug date/time} + 49 \text{ hours} + 1 \text{ minute}$ (upper bound of the 48-hour postdose analysis window; see Table 7), if {DB study drug date and time are both nonmissing} and {medication date is complete and time is nonmissing}
- $DB \text{ study drug date} \leq \text{medication date} \leq DB \text{ study drug date} + 2 \text{ days}$, if {DB study drug date is nonmissing but time is missing} or {medication date is complete but time is missing}.

Thus, DBT rescue medications are a subset of DBT concomitant medications.

OLE Rescue Medications

OLE rescue medications are defined as OL rimegepant concomitant medications from the Rescue Medications CRF that meet any of the following criteria:

- OL rimegepant date/time < medication date/time < OL rimegepant date/time + 25 hours + 1 minute (upper bound of the 24-hour postdose analysis window; see Table 7), if {OL rimegepant date and time are both nonmissing} and {medication date is complete and time is nonmissing}
- OL rimegepant date ≤ medication date ≤ OL rimegepant date + 1 day, if {OL rimegepant date is nonmissing but time is missing} or {medication date is complete but time is missing}.

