6.3.3.2 Rescue Medication Use Within 24 Hours Postdose During the DBT Phase

Analyses are based on the evaluable DBT efficacy analysis set, i.e., subjects in the DBT efficacy analysis set with first DBT rescue medication date \leq DB study drug date + 1 day and missing first DBT rescue medication time are excluded.

Time to first DBT rescue medication use is defined as (first DBT rescue medication date/time – DB study drug date/time) in hours (see Section 7.1). Rescue medication use within 24 hours postdose during the DBT Phase is defined as time to first DBT rescue medication use \leq 24 hours.

Treatment Group Comparisons

The percentage of subjects with rescue medication use within 24 hours postdose is compared between treatment groups using analogous methods as the main analysis of the primary endpoint, except that the NC=F and RM=F methods are not applied because they are not applicable to this endpoint (see Section 6.3.2.1).

Time to Rescue Medication Use Through 24 Hours Postdose

Time to rescue medication use through 24 hours postdose is assessed by treatment group as follows:

- Kaplan-Meier plot and table using 2-hour time intervals (i.e., 0 to ≤ 2 , >2 to ≤ 4 , ..., >24). The Kaplan-Meier plot displays the percentage of subjects taking rescue medication within 24 hours postdose on the y-axis versus time in hours on the x-axis.
- Time-to-event distribution table (hours).

See Section 6.1.1.1 for time-to-event plot and table attributes. Rescue medication use through 24 hours postdose is considered as an event in these time-to-event analyses. Subjects who do not take rescue medication within 24 hours postdose are censored at 24 hours and 1 minute (i.e., 1441 minutes).

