7.5.1 RM=F Algorithm During the DBT Phase

No DBT Rescue Medication Taken at or Before the Measurement in the X Analysis Window

No DBT rescue medication taken at or before the measurement in the X analysis window is defined as any of the following when the measurement is nonmissing in the X analysis window:

- No DBT rescue medication ever taken, i.e., missing first DBT rescue medication date (see Section 7.1)
- First DBT rescue medication date/time > {eDiary finding date/time for the measurement in the X analysis window}, if first DBT rescue medication time is not missing

- First DBT rescue medication date > {eDiary finding date for the measurement in the X analysis window}, if first DBT rescue medication time is missing.

DBT Rescue Medication Taken at or Before Time Point X (RM=F)

DBT rescue medication taken at or before time point X (RM=F) is defined as either (1) or (2):

- 1) DBT rescue medication taken at or before the measurement in the X analysis window. Defined as either of the following if the measurement is nonmissing in the X analysis window:
 - First DBT rescue medication date/time \leq {eDiary finding date/time for the measurement in the X analysis window}, if first DBT rescue medication time is not missing
 - First DBT rescue medication date \leq {eDiary finding date for the measurement in the X analysis window}, if first DBT rescue medication time is missing
- 2) DBT rescue medication taken at or before time point X and the measurement is missing in the X analysis window. Defined as either of the following:
 - (first DBT rescue medication date/time – reported DB study drug date/time) < upper bound of the X analysis window (see Table 7), if first DBT rescue medication time is not missing
 - First DBT rescue medication date \leq reported DB study drug date + Y days, if first DBT rescue medication time is missing
 - If X < 24 hours, then Y = 0.
 - If X = 24 hours, then Y = 1.
 - If X = 48 hours, then Y = 2.

Note that criterion (2) is used only in sensitivity analyses of the primary efficacy endpoint (see Section 6.3.2.2).

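### SAP 7.1 keeps only timed rescue records, so the missing-time rules in SAP 6.3.3.2 and 7.5.1 cannot operate and a subject with only untimed double-blind rescue is coded as never rescued

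*SAP*

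**What the plan says.** SAP 7.1 defines the first DBT rescue medication date/time and assigns it to two uses: key secondary endpoint 2 (rescue within 24 hours) and the DBT RM=F algorithm. The selection step reads "Records that meet the definition of DBT rescue medication are selected with both nonmissing medication date and time", the earliest such record is taken, and the entry closes with "Note that date and time are not imputed".

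Other parts of the SAP expect untimed records:

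- SAP 6.2.6.3 describes Rescue Medication CRF entries as "collected with both medication date and time (where time may be missing". Its definition of DBT rescue has a calendar-date rule (dosing date through dosing date plus 2 days) for use when "medication date is complete but time is missing".
- SAP 6.3.3.2 says that, for key secondary endpoint 2, subjects with a first rescue date no later than the dosing date plus 1 day "and missing first DBT rescue medication time are excluded".
- SAP 7.5.1 compares calendar dates when the first rescue has no time. It also gives this definition of a never-rescued subject: "No DBT rescue medication ever taken, i.e., missing first DBT rescue medication date".

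The next entry in 7.1, an imputed first rescue date/time for exploratory time-to-event analyses, requires only a date. SAP 7.1 also states that a missing time sorts ahead of a recorded time on the same date.

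**The concern.** A subject with a dated but untimed rescue record is a rescue user by the SAP's own definition. Under 7.1 the first-rescue variable for that subject is empty, and 7.5.1 reads an empty date as no rescue at all. The sections written to catch the case depend on the variable that has already dropped it.

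RM=F is the declared composite strategy for the primary endpoint and nine of the ten key secondary endpoints, and rescue use is the second key secondary endpoint in the fixed testing sequence. If it misses significance, endpoints 3 to 10 are reported descriptively only. One subject can therefore be a non-user, an exclusion or a failure, depending on which section is programmed. SAP 7 allows conventions to be changed in dataset specifications rather than in the SAP, so that choice could be made outside the plan.

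**Working it through.** **Plan's own figure.** With 270 per arm, 57.9% versus 43.9% and a two-sided 0.05 chi-square test, power is 0.904, which matches the stated approximately 90%. Nothing in this point changes it.

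**Logic check.** Take a dose on day 1 at 10:00, the 2-hour entry at 12:05 and the 24-hour entry on day 2 at 10:00. Apply 7.1, 6.3.3.2 and 7.5.1 twice: once as 7.1 is written, and once with untimed records kept and sorted first. KS2 is key secondary endpoint 2.

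| Rescue records | 7.1 as written | Untimed records kept |
|---|---|---|
| (a) Untimed, day 1 only | KS2 non-user; not rescued at 2 h or 24 h | KS2 excluded; RM=F at 2 h and 24 h |
| (b) Untimed day 1, plus timed day 1 15:00 | KS2 user; not rescued at 2 h, RM=F at 24 h | KS2 excluded; RM=F at 2 h and 24 h |
| (c) Untimed day 1, plus timed at 34 h | KS2 non-user; not rescued at 2 h or 24 h | KS2 excluded; RM=F at 2 h and 24 h |
| (d) Untimed, day 2 only | KS2 non-user; not rescued at 2 h or 24 h | KS2 excluded; not rescued at 2 h, RM=F at 24 h |

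Three things follow.

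1. Under 7.1 as written, the missing-time rules never fire.
2. A subject who also has a timed record is moved to that time rather than lost (b, c).
3. Reviving the 6.3.3.2 exclusion unchanged is no cure. Only rescue users can meet it, so it removes events and never non-events. In (b) it would discard a subject with a timed rescue 5 hours after dosing. SAP 3.2.2.1 defines this endpoint on the DBT efficacy set without such an exclusion.

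**Size, by assumption.** Let q be the true 24-hour rescue rate in an arm and u the share of users with only untimed records, equal in both arms. Coding them as never rescued gives q(1−u). Excluding them gives q(1−u)/(1−qu). Differences are placebo minus rimegepant, in points.

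| Assumed q, placebo vs rimegepant | u | True | Never rescued | Excluded |
|---|---|---|---|---|
| 35% vs 20% | 2% | 15.0 | 34.30 − 19.60 = 14.70 | 14.86 |
| 35% vs 20% | 5% | 15.0 | 33.25 − 19.00 = 14.25 | 14.65 |
| 35% vs 20% | 10% | 15.0 | 31.50 − 18.00 = 13.50 | 14.28 |
| 35% vs 25% | 10% | 10.0 | 31.50 − 22.50 = 9.00 | 9.57 |

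In the last row, power at 270 per arm falls from 0.719 to 0.654 under never-rescued coding. In the third row it falls from 0.976 to 0.955.

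For the endpoints sustained to 24 hours, the ceiling on false responders at u = 10% is 0.10 × 35% = 3.5% on placebo and 0.10 × 20% = 2.0% on rimegepant. The real figure would be lower, because many of these subjects fail on reported pain or function.

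**The case against.** The strongest reply is that the SAP does not clearly plan to treat these subjects as never rescued. Sections 6.3.3.2 and 7.5.1 say otherwise, and the sorting rule in 7.1 presupposes untimed records. That stands: this is a contradiction within the SAP, and the harm follows only if 7.1 is programmed literally. The contrast with the imputed variable beside it, which asks only for a date, makes the literal reading a natural one.

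A reader might infer several stronger points that the documents do not support.

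- **Every RM=F endpoint is affected.** No. OLE RM=F (SAP 7.5.2) uses all OLE rescue records and has its own date-only rule. Time to pain relief (SAP 6.3.5.2) uses the imputed variable.
- **The primary endpoint is compromised.** It is little exposed. Protocol 5.5.2.1 and 6.4.4 bar rescue before 2 hours, and 5.5.2.1 also requires the 2-hour entry to be complete. A compliant same-day rescue therefore came after the primary measurement. Reviving the date-only branch without qualification would make such a subject a primary failure, which is a new error.
- **Most untimed users become sustained responders.** Many would fail anyway, because Protocol 5.5.2.1 allows rescue for unrelieved symptoms or returning moderate or severe pain. This protection is incomplete: no entries are scheduled between 8 and 24 or between 24 and 48 hours, so relapse and rescue in a gap can leave every recorded score favourable.
- **Acute medication on the Concomitant Medications CRF should also count as rescue.** The SAP definition begins "DBT rescue medications are defined as DBT concomitant medications from the Rescue Medications CRF that meet any of the following criteria", whereas the protocol has the broader-sounding "In the DBT Phase, rescue medication includes acute migraine medication (permitted or exclusionary" and adds a time window. But Protocol 6.4.4 also defines rescue by purpose and sends it to the rescue diary. A date-only sweep of the other form would capture permitted pre-dose use for mild attacks and use after the 48-hour entry, and so change the estimand.

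**Conclusion.** The point holds as an internal contradiction with a wrong result under literal programming. A subject whose only DBT rescue records are dated but untimed is coded as a non-user in key secondary endpoint 2 and as not RM=F in the DBT binary endpoints, mainly sustained endpoints 4 to 9. The DBT percentage in the reliability comparison is affected too. It can be too high relative to OLE percentages computed under a working date rule, which works against showing reliability.

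The size cannot be determined, because the documents give neither the rescue rates nor the share of untimed records. If the untimed share is equal in both arms and rescue is commoner on placebo (both assumptions), the bias in key secondary endpoint 2 is toward the null: for example 15 to 13.5 points at 35% versus 20% with 10% untimed. Unequal shares could move it either way. A reader might infer inflated type I error in favour of rimegepant; nothing in the documents shows that.

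**What to change.** 1. In SAP 7.1, select DBT rescue records with a nonmissing date and leave the time missing where it was not recorded. The existing sorting rule then places them first, and the date rules in 7.5.1 operate.
2. In SAP 6.3.3.2, replace the exclusion. Count an untimed rescue dated on the dosing date as an event, since rescue follows dosing and is then necessarily within 24 hours. For an untimed next-day rescue, where the timing is ambiguous, state one rule and run a sensitivity analysis with the other. A timed record at or before 24 hours should count as an event whatever untimed records exist.
3. In SAP 7.5.1, state how untimed same-day rescue is handled at time points up to 2 hours, with a sensitivity analysis. Otherwise the date-only branch turns an evening rescue into a primary failure.
4. Report the number of untimed-only rescue users by arm.
5. Leave the restriction to Rescue Medication CRF records as it is.

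The cost is one changed derivation, a few lines of SAP text, two small sensitivity analyses and one count. It should be settled in the SAP itself, not in dataset specifications, and before treatment codes are opened.
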